Ultrasound Evaluation of Crohn's Disease

NCT03235180

September 28, 2017

IRB Minimal Risk Protocol Template

General Study Information

Principal Investigator: [name], [name], [name]

Study Title: Ultrasound Evaluation of Crohn's Disease

Protocol version number and date: 9/28/17

Purpose

Hypothesis: Small bowel stiffness and vascularity measured by ultrasound imaging are useful biomarkers for Crohn's disease.

Aims, purpose, or objectives:

The overall goal is to investigate the value of ultrasound measurements of small bowel stiffness and vascularity as new biomarkers for Crohn's disease.

Background (*Include relevant experience, gaps in current knowledge, preliminary data, etc.*):

Crohn's Disease (CD) is a chronic inflammatory condition in the bowel that affects over 1 million Americans, costing billions of dollars every year. Due to the relapsing nature of the disease, frequent imaging follow-ups are often necessary over many years to monitor treatment response to guide therapy adjustments. An ideal CD imaging method should be able to evaluate both inflammation and fibrosis, as patients with predominantly inflammatory lesions are more likely to respond to medical therapy, while patients with fibrostenotic lesions usually require surgery. Ultrasound is safe, cost-effective, and widely accessible, thus provides an attractive alternative to the clinical standard Computed Tomography (CT, risks of radiation) and Magnetic Resonance Imaging (MRI, more expensive and limited accessibility). Because ultrasound may not be able to image bowel loops deep in the body, its main role is to follow-up after initial screening by CT or MRI (especially for terminal ileum, which is easily accessible by ultrasound and the most frequently affected bowel segment for CD).

In this project, we will study the efficacy of ultrasound shear wave elastography and vascularity imaging for CD evaluation. Literature evidences demonstrate that bowel stiffness is correlated with fibrosis, while bowel vascularity and perfusion is correlated with inflammation. Therefore, we expect the combination of shear wave elastography and vascularity imaging can increase the sensitivity and specificity of CD evaluation.

Aim 1: To evaluate the correlation of ultrasound measurements with clinically indicated Magnetic Resonance Enterography (MRE).

Aim 2: To investigate if ultrasound measurements can be used to predict treatment response for Crohn's disease.

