Street address, city, county, precinct, zip code, and their equivalent geocodes		
Phone or fax numbers		
Account, member, certificate or professional license numbers, health beneficiary numbers		
Vehicle identifiers and serial numbers, including license plate numbers		
If None of the above identifiers will be recorded or maintained in the dataset and/or sent outside of the study team, please check "None".	 None	 None

Statistical Information

Note: Power analyses and study endpoints are not needed for a pilot or feasibility studies.

No statistical information. *If checked, please explain:*

Statistical Considerations

Power Statement:

The sample-size for the present investigation was determined for the primary aim of assessing the correlation between ultrasound parameters and the MaRIA score (a score calculated from MR enterography, which reflects bowel inflammation [1]). For ultrasound to have meaningful clinical utility we would require a correlation with MaRIA score of at least 0.70. For the primary analysis, the correlation between ultrasound measurements and MaRIA score will be compared to 0.70 using a two-tailed, alpha=0.05 level test. Under the assumption that the “true” correlation is 0.82, a sample-size of N=100 will provide statistical power of 82% for the primary analysis.

Data Analysis Plan:

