Disease activity measurements will be obtained via MR enterography at baseline and 6-months following treatment, and via ultrasound at baseline, 4-weeks and 6-months after treatment. Two quantitative ultrasound parameters will be obtained: A) shear wave speed obtained from the GE Logiq E9; B) vessel density (the percentage of pixels in the bowel lesion with blood flow compared to the total area of the lesion) obtained from the Verasonics. For each ultrasound parameter, the mean of all repeated measurements will be used as the representative value for a given patient at a given time. Measurements obtained following baseline will be expressed as percentage change from baseline. For inflammation evaluation, the correlation of each ultrasound parameter with MaRIA score will be assessed using a point estimate and 95% confidence interval. In addition, using a MaRIA cut-point of 11, patients will be categorized as having mild versus severe disease [1]. As a secondary analysis, logistic regression with corresponding ROC (Receiver Operating Characteristic) analysis will be used to assess whether ultrasound measurements can distinguish between mild versus severe inflammation. Findings from these analyses will be summarized using the point-estimate and 95% confidence interval for the area under the ROC curve (AUROC). In addition to univariate analyses, exploratory multivariable analyses will be performed to assess whether combination of ultrasound parameters can increase the performance relative to the univariate findings. Similar analyses will be performed to assess whether ultrasound parameters are useful for fibrosis evaluation: for these analyses, the MR enterography percentage gain change (PGC) will be used for correlation analysis, and a PGC cut point of 23.5% will be used to categorize fibrosis as mild or severe for ROC analysis [2].

For Aim 2, a series of analyses will be performed to assess whether ultrasound parameters obtained at baseline and 4-weeks can predict 6-month treatment outcome. A correlation analysis will be performed to assess the association of the percentage change in ultrasound parameters from baseline to 4-weeks with the percentage change in MaRIA score from baseline to 6-months. In addition, treatment outcome will be dichotomized (responder, non-responder) based on the 6-month MR enterography. Univariable and multivariable logistic

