regression with corresponding ROC analyses will be used to assess whether percentage change in ultrasound measurements at 4-weeks can predict treatment outcome. Findings from these analyses will be summarized using the point-estimate and 95% confidence interval for the AUROC. In all cases, distributional assumptions will be evaluated with transformations or non-parametric methods used as appropriate. Two-tailed p-values < 0.05 will be considered statistically significant.

Endpoints

Primary: please see detailed description above.

Secondary: please see detailed description above.

References:

1. Rimola, J., et al., *Magnetic Resonance Imaging for Evaluation of Crohn's Disease: Validation of Parameters of Severity and Quantitative Index of Activity*. Inflammatory Bowel Diseases, 2011. **17**(8): p. 1759-1768.
2. Rimola, J., et al., *Characterization of Inflammation and Fibrosis in Crohn's Disease Lesions by Magnetic Resonance Imaging*. American Journal of Gastroenterology, 2015. **110**(3): p. 432-440.

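### The plan names no internal validation and no test of added value for the combined ultrasound models, so apparent AUROC would modestly favour the combination

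*Combined protocol and SAP*

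**What the plan says.** The Background sets the expectation: "we expect the combination of shear wave elastography and vascularity imaging can increase the sensitivity and specificity of CD evaluation".

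The Data Analysis Plan names the candidate predictors: "Two quantitative ultrasound parameters will be obtained", namely shear wave speed and vessel density. For Aim 1, inflammation is split at a MaRIA score of 11 and fibrosis at a PGC of 23.5%. Each parameter is assessed alone by logistic regression with ROC analysis. Multivariable analyses, labelled exploratory, are then to "assess whether combination of ultrasound parameters can increase the performance relative to the univariate findings".

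For Aim 2, patients are classed as responders or non-responders from the 6-month MR enterography. Models with a single parameter and models with several are both planned, and their purpose is stated as follows: "regression with corresponding ROC analyses will be used to assess whether percentage change in ultrasound measurements at 4-weeks can predict treatment outcome". This sentence does not carry the exploratory label, and it does not state a comparison of the combination with single parameters.

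In both aims the results are to be summarised by the AUROC and its 95% confidence interval. A general two-tailed 0.05 significance rule closes the section. The plan mentions no bootstrap, cross-validation or split sample, no interval or test for a difference in AUROC, and no criterion for added value. It gives neither a responder definition nor an expected response rate.

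**The concern.** A logistic model with two parameters, fitted and scored on the same patients, gives an AUROC that is on average higher than the same model would achieve in new patients. Much of that excess comes from fitting the second coefficient to noise, which a single-parameter analysis does not do. Setting the two apparent AUROCs side by side therefore tilts the comparison towards the combination, even when the second parameter carries no information.

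This matters because added value from the combination is the result the Background says is expected. The yardstick named in the plan leans towards confirming it. The Aim 2 models are meant to support prediction of treatment response, so an inflated AUROC there would be read as predictive performance.

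**Working it through.** **The plan's own figure.** The only computed figure is the power of the primary correlation test: "a sample-size of N=100 will provide statistical power of 82% for the primary analysis", for a true correlation of 0.82 against 0.70 at two-sided alpha 0.05. By Fisher's z:

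- atanh(0.82) − atanh(0.70) = 1.1568 − 0.8673 = 0.2895
- 0.2895 × √(100 − 3) = 2.851
- Power = Φ(2.851 − 1.960) = Φ(0.891) = 81.4%

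This agrees with the stated 82%. The plan states no figure for the AUROC or combination analyses, so their behaviour was simulated.

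**Simulation inputs.**

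- N = 100 (Power Statement).
- Two parameters (Data Analysis Plan).
- Assumed: normally distributed parameters; a first parameter with true AUROC 0.70 (0.50 and 0.80 also run); a second parameter that is pure noise, independent of the first.
- Assumed: 10, 20, 30 or 50 patients in the smaller outcome group, since the plan gives no split for any binary outcome.
- Maximum-likelihood logistic fits, at least 2,000 simulated trials per setting.

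Optimism = mean apparent AUROC of the fitted combination − mean true AUROC of that same fitted combination.

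**Two parameters, the second worthless, first-parameter AUROC 0.70:**

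| Smaller group | Apparent AUROC | True AUROC | Optimism | Combination beats the better single parameter |
|---|---|---|---|---|
| 10 | 0.718 | 0.675 | 0.043 | 70% |
| 20 | 0.711 | 0.687 | 0.024 | 72% |
| 30 | 0.709 | 0.691 | 0.019 | 73% |
| 50 | 0.706 | 0.692 | 0.014 | 72% |

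The first parameter alone has a true AUROC of 0.70. The fitted combination is thus slightly worse in truth (0.675 to 0.692) while appearing slightly better (0.706 to 0.718).

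**Other signal strengths.** At a first-parameter AUROC of 0.80, optimism is about 0.02 with 10 in the smaller group, 0.014 with 20, 0.011 with 30 and 0.009 with 50. With no signal in either parameter it runs from 0.07 (50) to 0.12 (10). Across all settings the combination strictly beats the better single parameter in about 64% to 73% of trials, or 66% to 77% counting ties.

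**Does the remedy work?** Bootstrap optimism correction was applied to the AUROC gain of the combination over the first parameter (AUROC 0.70; 150 simulated trials with 60 resamples each):

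| Smaller group | Mean apparent gain | Mean corrected gain | Trials showing a gain: apparent → corrected |
|---|---|---|---|
| 10 | +0.019 | −0.009 | 77% → 29% |
| 20 | +0.010 | −0.011 | 71% → 22% |
| 50 | +0.009 | −0.007 | 81% → 24% |

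A likelihood-ratio test of the worthless second parameter at the 5% level rejects in 4.8% to 5.1% of trials.

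**The case against.** The case against has five parts.

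1. **The plan does not say the models will be scored in-sample.** It is silent, and its significance rule can be read as covering the coefficient of the added parameter. This stands as a limit: the bias arises only if the plan is carried out with nothing beyond what is written. The silence is still a gap, because the named summary would be satisfied by apparent AUROC alone.

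2. **The explicit comparison is exploratory and belongs to Aim 1.** This stands and limits the consequence. The Aim 2 models carry no such label, so an inflated AUROC is possible there too, but the plan states no combination-versus-single comparison for that aim.

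3. **The optimism is small beside the sampling error.** At AUROC 0.70 with 50 against 50, the Hanley–McNeil standard error is 0.052, so the 95% half-width is 1.96 × 0.052 ≈ 0.10, against optimism of 0.014. This stands for the AUROC itself. It does not remove the one-sided tilt in a comparison made on the same patients.

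4. **An in-sample gain need not be false.** If the two parameters are correlated, one that does not discriminate alone can still add information. At a correlation of 0.5 the true gain was about 0.01 to 0.02. This stands, and it is a reason for a proper test of the added parameter.

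5. **Stronger readings go beyond the documents.** A reader might infer that the combination would nearly always look better. That does not fit two parameters; shares of about 92% to 93% appear only when four predictors are entered. A reader might get to four by counting baseline and 4-week values separately, or pre- and post-contrast images separately. But the plan expresses post-baseline values as percentage change, names the 4-week change as the Aim 2 predictor, and nowhere enters both contrast states in one model. A reader might also infer that responders will be few. No rate is given, and what drives the bias is the smaller group, which could be the non-responders.

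**Conclusion.** The concern holds as a minor gap. For the two parameters the plan names, following the text with nothing added favours the combination in roughly two-thirds to three-quarters of trials when the second parameter is worthless.

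With a single-parameter AUROC of 0.70 to 0.80, apparent AUROC is overstated by about 0.01 to 0.025 with 20 to 50 patients in the smaller outcome group, and by about 0.02 to 0.04 with 10. With no true signal the overstatement is 0.07 to 0.12. For balanced groups and a useful first parameter it is about 0.01.

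These sizes rest on N = 100, an independent noise parameter, and assumed group sizes and signal strengths that the documents do not supply. They would be larger only if more than the two named parameters were entered, which the documents do not establish. The primary correlation analysis and its power are not affected.

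**What to change.** Add to the Data Analysis Plan, for every multivariable model in Aims 1 and 2:

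- Report the bootstrap optimism-corrected AUROC, refitting the whole model in each resample, beside the apparent value.
- Judge added value by the likelihood-ratio test of the extra parameter in the nested logistic model, not by the difference between apparent AUROCs.
- List the predictors that enter each model, so that the two-parameter scope is explicit.

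The cost is a sentence or two, a few lines of code and a slightly lower reported AUROC. No extra patients or measurements are needed, and the Aim 1 multivariable analyses can stay exploratory.

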Subject Information – charts, records, images, or specimens are considered ‘subjects’

Target accrual is the proposed number of subjects to be included in your study at your site. “Subjects” may include Mayo Clinic charts, records, or specimens, and/or charts, records, or specimens received at Mayo Clinic from external sources for collaborating analysis by the investigator under this IRB application:

Target accrual: 100

Subject population: patients with confirmed or suspected Crohn’s disease.

Inclusion criteria: Crohn’s disease patients with involvement of terminal ileum (thickness > 3mm) or other segments of small or large bowel, age above 18.,

Exclusion criteria: patients with change of medicine or going to surgery over the 6-months follow-up period, patients with unreliable ultrasound images due to conditions such as large body habitus or poor ultrasound imaging window; adults lacking capacity to consent; vulnerable subjects such as prisoners. Pregnant women, nursing mothers, patients with known or suspected right-to-left, bi-directional, or transient right-to-left cardiac shunts, patients with history of hypersensitivity allergic reactions to ultrasound contrast agents.

Yes No Will a Certificate of Confidentiality (COC) be obtained from NIH? If yes,

Who is obtaining the COC: Mayo Clinic investigator, study sponsor, other:

Explain why a COC is needed:

Study Design

Methods: *Describe, in detail, the research activities that will be conducted under this protocol:*

Study Design: We will study the terminal ileum of 100 Crohn’s disease patients to investigate the efficacy of ultrasound measurements for disease evaluation and treatment outcome prediction. Patients with ongoing medical therapy or starting a new medical therapy will be recruited. Inflammation and fibrosis evaluated by contrast enhanced MR enterography at baseline and 6-months post therapy will be used as the reference standard. Ultrasound will be performed at baseline, 4-weeks, and 6-months. For Aim 1, correlation of ultrasound measurements with MR enterography results will be evaluated at baseline and 6-months. For Aim 2, we will assess the association of the percentage change in ultrasound parameters from baseline to 4-weeks with the percentage change in MR enterography scores from baseline to 6-months. More information about data analysis can be found in the statistical section below.

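### Ultrasound is related to MaRIA and to PGC only separately, so a stiffness–PGC association cannot by itself be attributed to fibrosis rather than accompanying inflammation

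*Combined protocol and SAP*

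**What the plan says.** - **Background.** The rationale is that "An ideal CD imaging method should be able to evaluate both inflammation and fibrosis", because predominantly inflammatory lesions and fibrostenotic lesions are managed differently. The roles of the two ultrasound measures are taken from the literature: "bowel stiffness is correlated with fibrosis, while bowel vascularity and perfusion is correlated with inflammation".
- **Data Analysis Plan, Aim 1.** Each parameter (shear wave speed, vessel density) is correlated with MaRIA, with ROC analysis at a MaRIA cut of 11. Then "Similar analyses will be performed to assess whether ultrasound parameters are useful for fibrosis evaluation", with PGC as the correlate and a PGC cut of 23.5% for ROC. The multivariable step is exploratory and combines ultrasound parameters as predictors. No analysis contains both MaRIA and PGC, stratifies by one of them, or compares a parameter's correlation with one against its correlation with the other.
- **Criteria.** The Power Statement sets a utility bar for inflammation only: "we would require a correlation with MaRIA score of at least 0.70". For PGC there is no stated bar beyond the estimate, its 95% CI and the general two-tailed 0.05 level.
- **Aim 2.** Study Design names inflammation and fibrosis on MRE as the reference standard and relates 4-week ultrasound change "with the percentage change in MR enterography scores from baseline to 6-months". The Data Analysis Plan correlates it "with the percentage change in MaRIA score from baseline to 6-months". The responder outcome is based on the 6-month MRE, with no measure named.

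**The concern.** One lesion can carry both processes; the Background itself speaks of lesions that are predominantly inflammatory. MaRIA and PGC may therefore be correlated across patients. If so, a parameter that responds only to inflammation will also correlate with PGC, and the planned analysis cannot tell this apart from real fibrosis information. The same holds in reverse for vessel density and MaRIA. At stake is the reading of the fibrosis result. A significant stiffness–PGC correlation would naturally be taken as support for stiffness as a fibrosis marker, and the plan contains nothing that tests that reading.

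**Working it through.** **Inputs.** From the Power Statement: the ultrasound–MaRIA correlation "will be compared to 0.70 using a two-tailed, alpha=0.05 level test", with the assumed true "correlation is 0.82, a sample-size of N=100" and stated power of 82%. From the end of the statistical section: two-tailed p<0.05. Assumed, because the documents do not give them: r(MaRIA,PGC), from 0 to 0.7, and r(stiffness,MaRIA), from 0.3 to 0.82. The 0.82 is the plan's figure for ultrasound measurements in general, not for stiffness.

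**1. The plan's own figure.** By Fisher z, power = Φ[(atanh 0.82 − atanh 0.70)·√(100−3) − 1.96] = 81.4%; simulation gives 82.3%. The stated 82% reproduces, and nothing below changes it.

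**2. Correlation induced by inflammation alone.** Suppose stiffness (S) has no link to PGC (G) given MaRIA (M). Then r(S,G) = r(S,M) × r(M,G). For example, 0.5 × 0.3 = 0.15, 0.82 × 0.1 = 0.082 and 0.82 × 0.7 = 0.574.

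**3. Chance of p<0.05 at N=100.** With m = atanh(r)·√97, the chance is Φ(m − 1.96) + Φ(−m − 1.96).

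| r(S,M) | r(M,G)=0 | 0.1 | 0.2 | 0.3 | 0.5 | 0.7 |
|---|---|---|---|---|---|---|
| 0.3 | 5% | 6% | 9% | 14% | 32% | 56% |
| 0.5 | 5% | 8% | 17% | 32% | 71% | 95% |
| 0.7 | 5% | 11% | 28% | 56% | 95% | >99% |
| 0.82 | 5% | 13% | 37% | 70% | 99% | >99% |

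Simulation of the nine cells with r(S,M) of 0.5–0.82 and r(M,G) of 0.3–0.7 agrees within 1.2 percentage points. In those cells, splitting PGC at its median (an assumption; the plan's cut is 23.5%) gives a mean AUROC of 0.57 to 0.77.

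**4. Does the planned multivariable step fill the gap?** Take vessel density as correlated 0.82 with MaRIA (assumed). Adjusting the stiffness–PGC correlation for vessel density still leaves significance in 8% to 88% of simulated trials over the same nine cells. An imperfect ultrasound proxy for inflammation does not replace MaRIA.

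**5. Adjusting for MaRIA.** The partial correlation is [r(S,G) − r(S,M)·r(M,G)] / √[(1 − r(S,M)²)(1 − r(M,G)²)]. Its numerator is zero in the scenario of step 2. Tested by Fisher z with √(100−4), the simulated rate is 4.6% to 5.4% in all nine cells.

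**6. If MaRIA measures inflammation with error.** Let reliability be ρ, keep the observed r(S,M) and r(M,G), and let stiffness and PGC depend on true inflammation only. Then r(S,G) = r(S,M)·r(M,G)/ρ, and the partial correlation is r(S,M)·r(M,G)·(1/ρ − 1) / √[(1 − r(S,M)²)(1 − r(M,G)²)]. At ρ=0.9 with 0.82 and 0.7, this is 0.574 × 0.111 / 0.409 = 0.156, significant about 34% of the time. Over the nine cells the range is about 5–34% at ρ=0.9 and about 7–95% at ρ=0.8. Adjustment improves on the marginal analysis but is not a clean 5%.

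**The case against.** The case against is substantial.

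- **Aim 1 asks for correlation with MRE, and marginal estimates answer it.** An association carried by inflammation still predicts PGC; it misleads only if read as specific to fibrosis. No aim or endpoint claims that stiffness is fibrosis-specific. This stands: a reader might infer that the planned fibrosis analysis is invalid, and the documents do not support that.
- **The size is assumed.** The MaRIA–PGC correlation is not in the documents, 0.82 is not assigned to stiffness, and the scenario gives stiffness no fibrosis link at all, although the Background reports one. This stands, and is why the table runs down to zero. A reader might infer that a false fibrosis claim is near certain; only the upper part of an assumed range says so.
- **Significant is not the same as useful.** If the 0.70 bar carried over to PGC, an observed r of at least 0.70 would occur in at most 1.8% of trials for r(M,G) up to 0.7 and r(S,M) up to 0.82. Both correlations would also be reported and could be compared. But the bar is written for MaRIA only, and no such comparison is planned.
- **Adjustment is imperfect.** Step 6 confirms it. A tempting stricter rule, naming a marker only when its partial correlation excludes zero, would be unreliable under measurement error and sets no minimum useful size. It is not recommended.
- **Aim 2 may be consistent.** MaRIA is the only MRE measure the documents call a score, and the Background ties response to medical therapy to inflammatory lesions. A reader might infer that fibrosis was wrongly left out of Aim 2, but the responder outcome is not limited to MaRIA. What remains is an ambiguity to reconcile.
- **The fibrosis analysis is not the powered primary, and adjusted estimates could be computed later.** True, but specificity claims carry more weight if the analysis behind them was fixed in advance.

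**Conclusion.** The concern holds in a limited form. The plan never adjusts one MRE measure for the other, so its fibrosis analysis supports a statement that stiffness correlates with PGC, not that stiffness reflects fibrosis independently of inflammation. If stiffness carried no fibrosis information beyond MaRIA, the chance of a significant PGC correlation at N=100 would run from 5% (MaRIA and PGC uncorrelated), through about 13% (MaRIA–PGC 0.1, stiffness–MaRIA 0.82), to 32% to over 99% (MaRIA–PGC 0.3–0.7, stiffness–MaRIA 0.5–0.82). These figures rest on that no-link scenario, on approximate normality, and on correlations the documents do not supply. The sample size, the stated power and the MaRIA primary analysis are unaffected. The Aim 2 wording is a minor, secondary matter.

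**What to change.** Keep the planned marginal correlations and ROC analyses. In the Data Analysis Plan, add wording such as:

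> *As prespecified secondary analyses, the partial correlation of shear wave speed with PGC given MaRIA, and of vessel density with MaRIA given PGC, will be estimated with 95% confidence intervals. Any statement that a parameter is specific to fibrosis or to inflammation will rest on these adjusted estimates and will note that residual confounding remains if MaRIA or PGC is measured with error.*

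Regressing each ultrasound parameter on both MRE measures would serve equally well.

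For Aim 2, reconcile Study Design with the Data Analysis Plan on which MRE measures enter the change analysis, for example by also reporting the correlation of 4-week ultrasound change with 6-month PGC change.

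The cost is small: no new patients, visits or measurements. One covariate costs one degree of freedom. The correlation detectable with 80% power at N=100 is tanh[(1.96 + 0.84)/√96] = 0.278 for a partial correlation, against tanh[(1.96 + 0.84)/√97] = 0.277 for a marginal one. The real downside is that adjusted estimates may look less favourable than marginal ones.

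### Aim 2 models shear wave speed and vessel density together only on a dichotomised responder outcome; a two-parameter model on percentage change in MaRIA, already collected, would test the added value of the second parameter with more power

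*Combined protocol and SAP*

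**What the plan says.** The Background section (under Purpose) makes the joint value of the two techniques a question of the study: "we expect the combination of shear wave elastography and vascularity imaging can increase the sensitivity and specificity of CD evaluation".

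For Aim 2, the Data Analysis Plan lists two analyses:

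- **Continuous outcome.** "A correlation analysis will be performed to assess the association of the percentage change in ultrasound parameters from baseline to 4-weeks". The outcome here is the 6-month percentage change in MaRIA, and no multivariable model is attached to it.
- **Binary outcome.** "treatment outcome will be dichotomized (responder, non-responder) based on the 6-month MR enterography. Univariable and multivariable logistic". These models come with ROC curves, and their stated purpose is to see if the early ultrasound changes predict response. Results are reported as AUROC with a 95% confidence interval.

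The plan gives no cut-off for responder status, no expected response rate, no Aim 2 effect size and no Aim 2 power. It names no test of the increment from the second parameter in Aim 2.

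For Aim 1 the corresponding sentence reads: "exploratory multivariable analyses will be performed to assess whether combination of ultrasound parameters can increase the performance relative to the univariate findings". It does not say which outcome scale is meant.

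**The concern.** A correlation takes one ultrasound parameter at a time. In Aim 2 both parameters therefore meet in one model only on the responder scale, where all differences in MaRIA change within each class are discarded. No reason is given for leaving the continuous outcome out of the joint analysis.

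At stake is the conclusion about the second parameter. If it carries a moderate amount of extra information, an analysis of 100 patients on a binary outcome will often miss it. The study could then report that one measurement is enough, when the outcome scale and not the data produced that result.

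**Working it through.** **1. The plan's own power figure.** The Power Statement compares a true correlation of 0.82 with 0.70 at N=100, and the correlation "will be compared to 0.70 using a two-tailed, alpha=0.05 level test". By Fisher's z:

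power = Φ[(atanh 0.82 − atanh 0.70)·√(100−3) − 1.96] = Φ[(1.1568 − 0.8673)·9.849 − 1.96] = Φ(0.891) = 81.4%.

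The stated 82% is reproduced. It concerns the primary analysis and says nothing about Aim 2.

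**2. Inputs for Aim 2.**

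- From the documents: N=100, and the two-sided 0.05 level ("Two-tailed p-values < 0.05 will be considered statistically significant").
- Assumed: trivariate normal data; correlation 0.4–0.5 of the first parameter with the outcome; correlation 0.3 between the two parameters; 30% or 50% responders; responder status obtained by cutting the percentage change in MaRIA.
- Varied: the partial correlation ρ of the second parameter with the outcome, given the first.

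**3. Linear model, closed form.** Power ≈ Φ[atanh(ρ)·√(100−1−3) − 1.96], with √96 = 9.798:

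- ρ=0.20: Φ(0.2027·9.798 − 1.96) = Φ(0.026) = 51%
- ρ=0.25: Φ(0.2554·9.798 − 1.96) = Φ(0.543) = 71%
- ρ=0.30: Φ(0.3095·9.798 − 1.96) = Φ(1.073) = 86%
- ρ=0.35: Φ(0.3654·9.798 − 1.96) = Φ(1.621) = 95%

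**4. Simulation of both models.** There were 2,000 replicates per scenario. The correlation of the second parameter with the outcome was set to ρ·√[(1−r₁²)(1−r₁₂²)] + r₁·r₁₂, where r₁ is the first parameter's correlation with the outcome and r₁₂ the correlation between the parameters. The linear model used the partial F test and the logistic model the likelihood-ratio test.

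| ρ | Linear, continuous outcome | Logistic, responder outcome |
|---|---|---|
| 0.20 | 51–54% | 30–36% |
| 0.25 | 69–72% | 45–49% |
| 0.30 | 86% | 59–65% |
| 0.35 | 95–96% | 72–80% |

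The linear column agrees with step 3. Type I error was about 4–6% for both models, so the gain is not bought with false positives. Across repeated simulations, the loss within a scenario is roughly 15–28 points over these four rows.

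**5. Rough check of the binary column.** For small effects, a cut with event share p keeps a fraction φ(z_p)²/[p(1−p)] of the information. That is 0.3989²/0.25 = 0.637 at 50% and 0.3477²/0.21 = 0.576 at 30%. At ρ=0.25 the expected test statistic of 2.503 becomes 2.503·√0.637 = 1.997 (power 51%) or 2.503·√0.576 = 1.899 (power 48%). This approximation ignores the first parameter's effect, which lowers the logistic figures a little further.

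**6. How far the loss moves.**

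- ρ=0.10–0.15: about 4–12 points. ρ=0.40: 8–15. ρ=0.50: 1–4.
- ρ=0.20–0.30 with only 20% responders (correlation 0 or 0.5 between the parameters, first-parameter correlation 0.3 or 0.5): 24–35 points.
- ρ=0.20–0.30 with a first-parameter correlation of 0.7: 24–33 points.
- N=80 in place of 100, ρ=0.20–0.30, first-parameter correlation 0.3–0.5: about 12–28 points.
- Lognormal outcome left untransformed, ρ=0.20–0.30: 10–22 points at log-SD 0.6, and about 0–5 at log-SD 1.0.

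**The case against.** **The hypothesis is about sensitivity and specificity.** These need a binary outcome, so logistic regression with AUROC fits the Background's wording. This stands. A reader might infer that the linear model should replace the ROC analyses as the sole basis for the claim of added value. The documents do not support that: the two models answer different questions, and the linear one supplements.

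**No increment test is planned in Aim 2.** This also stands. The power figures refer to a coefficient or likelihood-ratio test of the second parameter, which the plan does not name. They measure what the binary scale can show about added value, and do not describe the failure of a planned test.

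**The continuous outcome is not discarded.** True for each parameter alone, since the correlation analysis is listed first. It remains unused for the two together.

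**The size is conditional.** A reader might take the loss as a fixed cost of the plan. It is not: every Aim 2 input except N and alpha is assumed, and step 6 shows losses from near zero to about 35 points.

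**Aim 1 may not share the limit.** The exploratory multivariable sentence follows the ROC text and speaks of performance, so a reader might infer that it too is confined to the cut-points. It can equally be read as covering the correlation analyses in the same paragraph. The text does not decide this, so no loss is claimed for Aim 1.

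**Conclusion.** The point holds for Aim 2. Both parameters enter one model only on the responder outcome, while a continuous outcome in the same patients is left to one-at-a-time correlations. Under the assumptions in step 2, the cost is roughly 15–28 points of power at partial correlation 0.20–0.35. It is about 1–15 points for weaker or stronger added effects, and it shrinks, close to nothing under heavy skew, when the outcome is analysed untransformed.

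The comparison is like for like only if responder status is a cut of MaRIA change. The plan says only that it is based on the 6-month MR enterography. If it rests on another feature, the two models have different outcomes and the power difference is not a pure loss. The case for a joint model on the continuous outcome remains.

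This is a worthwhile improvement to an aim that did not size the study. It is not a flaw in the primary analysis, whose requirement that "we would require a correlation with MaRIA score of at least 0.70" and whose stated 82% power are untouched.

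**What to change.** **Aim 2.** Add to the Data Analysis Plan a multiple linear regression of the percentage change in MaRIA from baseline to 6 months on the 4-week percentage changes in shear wave speed and vessel density together. Transform the outcome if it is skewed, as the plan's provision on distributional assumptions already allows. Report the partial F test for the second parameter and R-squared for one versus two parameters. Name this as the test of whether the second parameter adds predictive information. Keep the planned logistic/ROC analyses for the sensitivity and specificity question.

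**Aim 1.** State that the exploratory multivariable analyses include continuous MaRIA and continuous PGC as outcomes.

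**Cost.** One or two sentences and a few regression runs on data already collected, with no extra patients, visits or readings. The downside is one more model per outcome to report, with its assumptions to check.
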